## 8.2 Response Criteria

### **Evaluation of Target Lesions**

Complete Response (CR): Disappearance of all target lesions. Any pathological lymph nodes (whether target or non-target) must have reduction in short axis to <10 mm.

**Partial Response (PR):** At least a 30% decrease in the sum of the diameters of target lesions, taking as reference the baseline sum diameters.

**Progressive Disease (PD):** At least a 20% increase in the sum of the diameters of target lesions, taking as reference the smallest sum on study (this includes the baseline sum if that is the smallest on study). In addition to the relative increase of 20%, the sum must also demonstrate an absolute increase of at least 5 mm. (Note: the appearance of one or more new lesions is also considered progressions).

**Stable Disease (SD):** Neither sufficient shrinkage to qualify for PR nor sufficient increase to qualify for PD, taking as reference the smallest sum diameters while on study.

### **Evaluation of Non-Target Lesions**

**Complete Response (CR):** Disappearance of all non-target lesions and normalization of tumor marker level. All lymph nodes must be non-pathological in size (<10 mm short axis).

Note: If tumor markers are initially above the upper normal limit, they must normalize for a patient to be considered in complete clinical response.

**Non-CR/Non-PD:** Persistence of one or more non-target lesion(s) and/or maintenance of tumor marker level above the normal limits.

**Progressive Disease (PD):** Appearance of one or more new lesions and/or *unequivocal progression* of existing non-target lesions. *Unequivocal progression* should not normally trump target lesion status. It must be representative of overall disease status change, not a single lesion increase.

Although a clear progression of “non-target” lesions only is exceptional, the opinion of the treating physician should prevail in such circumstances, and the progression status should be confirmed at a later time by the review panel (or Principal Investigator).

### **Evaluation of Best Overall Response**

The best overall response is the best response recorded from the start of the treatment until disease progression/recurrence (taking as reference for progressive disease the smallest measurements recorded since the treatment started). The patient's best response assignment will depend on the achievement of both measurement and confirmation criteria.

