## 5.2 Concomitant Therapy

Relevant medical history should be obtained at screening and include prior medications and treatment history. All medications taken within 3 weeks prior to screening, regardless of indication, should be recorded

Use of any additional anti-neoplastic or anti-tumor agents not part of the study therapy, including chemotherapy, radiation therapy, immunotherapy, and hormonal anticancer therapy; these are not permitted while participating in this study. TAS-102 had minimal or no effect on the QTc interval; the drug was administered to 42 patients with advanced solid tumors with the recommended dosage regimen, but it had no large effect (i.e. > 20 ms) in the mean QTc interval when compared to placebo and no evident exposure-QT relationship was identified. Two of 42 patients (4.8%) had QTc greater than 500 msec and 1 of 42 patients (2.4%) had a QTc increase from baseline greater than 60 msec. The components of TAS-102 is not metabolized by the cytochrome P450 system, thus strong CYP inhibitors or inducers are not expected to have any effect on the metabolism of this drug. Study participants may receive additional investigational antineoplastic therapies upon completion of their participation in this protocol. Use of concurrent investigational agents is not permitted.

Any therapy or medication (except study drugs), administered from screening until 28 days after the last dose of either study drug, is considered a concomitant therapy or medication. However, if another course of anti-cancer therapy is initiated prior to the 28-day follow-up period visit; a record of concomitant medications will no longer be performed. If the use of any concomitant treatments (medications or procedures) becomes necessary, the treatment must be recorded, including the name of the drug or treatment, dose, route, date, indication for use, expected duration, and frequency of treatment. Assessment and documentation of concomitant medications will be done at each visit.

Subjects are prohibited from receiving the following therapies during the Screening and Treatment Phase of this trial:

- Antineoplastic systemic chemotherapy or biological therapy
- Immunotherapy not specified in this protocol

- Chemotherapy not specified in this protocol
- Investigational agents other than the study drug in this trial
- Radiation therapy

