*NOTE: Radiation therapy to a symptomatic solitary lesion may be considered on an exceptional case by case basis after consultation with sponsor-investigator. The subject must have clear measurable disease outside the radiated field. Administration of palliative radiation therapy will be considered clinical progression for the purposes of determining PFS.*

Live vaccines within 30 days prior to the first dose of trial treatment and while participating in the trial. Examples of live vaccines include, but are not limited to, the following: measles, mumps, rubella, chicken pox, yellow fever, rabies, BCG, and typhoid (oral) vaccine. Seasonal influenza vaccines for injection are generally killed virus vaccines and are allowed. However, intranasal influenza vaccines (e.g. Flu - Mist®) are live attenuated vaccines, and are not allowed.

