## 7.5 **Follow up/Survival**

Patients will be seen in follow-up at least every three months for the first three years after the initiation of therapy, or the date of death, whichever occurs first. Patients who are alive after three years will have follow up every six months for years four and five, then annual follow ups until date of death, or lost to follow up. Those patients who are lost to follow up will have every effort by telephone and mail to contact them for at least one month past their first missed clinic visit, with at least four documented attempts at contact to be made during that time.

Evaluation will consist of an interim medical history and a physical examination. Additional studies, such as labs (CBC and CMP), and any X-rays, or CT, PET/CT, bone scans or MRI scans used in evaluation of response will be repeated as clinically indicated. Other studies, such as, biopsies, will be performed as clinically indicated.

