#### Duration of Response

Duration of overall response: The duration of overall response is measured from the time measurement criteria are met for CR or PR (whichever is first recorded) until the first date that recurrent or progressive disease is objectively documented (taking as reference for progressive disease the smallest measurements recorded since the treatment started).

The duration of overall CR is measured from the time measurement criteria are first met for CR until the first date that progressive disease is objectively documented.

Duration of stable disease: Stable disease is measured from the start of the treatment until the criteria for progression are met, taking as reference the smallest measurements recorded since the treatment started, including the baseline measurements.

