#### **10.2 Period of Observation**

Following the subject’s written consent to participate in the study, all SAEs must be collected, including those thought to be associated with protocol-specified procedures. Collection of all SAEs must continue for 30 days after the last administration of the investigational product or until the start of new anti-tumor therapy, whichever comes first. If applicable, SAEs must be collected that relate to any later protocol-specified procedure (e.g., a follow-up skin biopsy). The investigator should notify the DISC of any SAE occurring after this time period that is believed to be related to the investigational product or protocol-specified procedure.

The investigator will begin collecting non-serious adverse event (NSAE) information at screening. This NSAE information should also be collected from the start of a placebo lead-in period or other observational period intended to establish a baseline status for the subjects. Treated subjects, including those who were prematurely discontinued from the study, will be followed for any adverse events that occur during the study until 30 days following the last dose of study treatment

(i.e., the Follow-up Visit). However, if another course of anti-cancer therapy is initiated prior to the 30-day follow-up period visit, collection of adverse events will no longer be performed, with the exception of events that may be possibly, probably, or definitely related to the investigational agent or are clinically significant.

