### **11.2 Analysis of Endpoints/Efficacy**

The primary endpoint to this study will be to document the objective rate of response by RECIST Criteria, version 1.1 of the participants in this trial which will be estimated along with exact 95% binomial confidence intervals.

The secondary endpoints of this study will be to determine the rate of development of toxicities, and the reversibility of toxicities of this regimen; the Objective Response Rate (by RECIST Criteria); the Clinical Benefit Rate (objective response + disease stability rate); the median duration of response in months, and the median Overall Survival.

A secondary endpoint of this study will be progression-free survival following TAS-102 therapy. Kaplan-Meier mean estimates and survival curves of progression-free survival rates will be calculated. Secondary endpoints include clinical benefit rate (CR + PR + SD), toxicities and reversibility of toxicities) will also be estimated along with exact 95% binomial confidence intervals.

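### The best-overall-response window does not close when a new anticancer therapy starts, so a response on the next drug could be counted for TAS-102

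*Combined protocol and SAP*

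**What the plan says.** **Response.** Section 8.2 (Evaluation of Best Overall Response) gives the window: "The best overall response is the best response recorded from the start of the treatment until disease progression/recurrence". The table that follows asks for confirmation at four weeks or more in non-randomized trials with response as the primary endpoint, which this trial is.

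**Durations.** Under Duration of Response, a response lasts "until the first date that recurrent or progressive disease is objectively documented". For stable disease: "Stable disease is measured from the start of the treatment until the criteria for progression are met". Neither mentions new therapy.

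**PFS.** Section 11.2 says only: "Kaplan-Meier mean estimates and survival curves of progression-free survival rates will be calculated". The one event rule is a note in 5.2: "Administration of palliative radiation therapy will be considered clinical progression for the purposes of determining PFS".

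**Stopping without progression.** Section 6.2 lists adverse events, non-compliance and interruptions over 21 days, among others. Sections 5.3.2 and 5.3.3 add delay and dose-reduction limits.

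**Later therapy.** The list of prohibited treatments in 5.2 covers the Screening and Treatment Phase. The same section states: "Study participants may receive additional investigational antineoplastic therapies upon completion of their participation in this protocol".

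**Scans after treatment.** The schedule in 7.1 marks tumour imaging under Follow Up but not under Off Treatment. Section 7.5 includes "bone scans or MRI scans used in evaluation of response will be repeated as clinically indicated".

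**Safety, by contrast.** Section 10.2 has a cut-off: "if another course of anti-cancer therapy is initiated prior to the 30-day follow-up period visit, collection of adverse events will no longer be performed", with an exception for related or clinically significant events. Section 5.2 likewise ends medication recording if new therapy begins before the 28-day visit.

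**The concern.** The response rate is meant to describe TAS-102. Take a patient with stable disease who stops for toxicity, starts another drug and then shrinks by 30% from the pre-TAS-102 baseline, with confirmation. No progression has occurred, so the window in 8.2 is still open and the patient is a responder as the rule is written. The protocol saw the need for a new-therapy cut-off in safety collection but gives none for efficacy.

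Two features make this matter more than its expected size suggests. Stage 1 (section 11.1) turns on a single response: none in 14 ends the study, one continues it. Duration of response will rest on very few patients, so one responder who switches drug and progresses much later could move the median. There is no concurrent control against which either would show.

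Later repair may also be impossible. No section asks for the start date of the next therapy, and 5.2 stops medication recording at about the moment that date would be needed.

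**Working it through.** **1. The plan's own figures (section 11.1).** With a true rate of 20%, the chance of 0/14 is 0.8^14 = 0.0440, below the stated 5% (0.8^13 = 0.0550, so 14 is the smallest number that meets it). The standard error with 30 patients is sqrt(p(1−p)/30): 7.3 points at p = 20% and at most 9.13 points at p = 50%, which agrees with the stated 9% after rounding. Both reproduce, and neither depends on this point.

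**2. Does the written rule admit a next-line response?** The steps are:
- stopping without progression is possible (6.2, 5.3.2, 5.3.3);
- the drug prohibition ends with the Treatment Phase (5.2);
- scans after treatment can serve response evaluation (7.1, 7.5);
- the window closes only at progression or recurrence (8.2).

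On-treatment scans come at every second cycle and follow-up visits at least every three months. For a patient who stops without progression, the next scan can therefore fall after a new drug has begun. Confirmation does not prevent this, because both scans can fall on the new drug.

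**3. Expected size.** Inputs:
- share f who stop without progression and switch: 10–20%, or 3–6 of 30. This is an assumption; the documents give no figure.
- next-line response rate r: up to 10%. Section 1.1 puts untargeted salvage agents below 10%.

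Extra responders are at most 3 × 0.10 = 0.3 to 6 × 0.10 = 0.6. Divided by 30, that is 1.0 to 2.0 points. One actual case is 1/30 = 3.3 points; for example, 3/30 = 10.0% (exact 95% CI 2.1–26.5%) becomes 4/30 = 13.3% (3.8–30.7%).

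**4. Stage 1.** If only TAS-102 non-responders can add a spurious response, the counted rate is p′ = p + (1−p)·f·r, and the chance of continuing is 1 − (1−p′)^14.

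| True p | f | r | Counted p′ | Continue, window closed | Continue, window open |
|---|---|---|---|---|---|
| 5% | 10% | 5% | 5.5% | 51.2% | 54.5% |
| 5% | 20% | 10% | 6.9% | 51.2% | 63.2% |
| 5% | 30% | 10% | 7.9% | 51.2% | 68.2% |
| 10% | 10% | 5% | 10.5% | 77.1% | 78.7% |
| 10% | 20% | 10% | 11.8% | 77.1% | 82.8% |
| 10% | 30% | 10% | 12.7% | 77.1% | 85.1% |

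These rows correspond to about 0.1 to 0.9 extra responders in 30. The values lie on the high side: they make no allowance for confirmation or for the evaluability rule in 11.1, and they assume that the spurious response is seen before the stage 1 decision.

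**5. Duration of response.** At a response rate of 10–20% there are 0.10 × 30 = 3 to 0.20 × 30 = 6 responders. The documents give no inputs from which to size a shift in the median.

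**The case against.** The case for leaving the text alone has real content.

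- **The path is narrow.** The patient must stop without progression, switch, be rescanned when scans are only as clinically indicated, reach a 30% decrease from the original baseline and have it confirmed. Section 6.3 replaces patients who simply choose to leave, and 11.1 requires two cycles for activity evaluation (8.1 says one, a separate conflict). This stands, and it keeps the expected effect below one responder in 30.
- **Other therapy is barred during participation.** This does not close the gap. The prohibition list in 5.2 is limited to the Screening and Treatment Phase, and both 5.2 and 10.2 foresee another anticancer course starting soon after TAS-102.
- **A late response would be visible.** Partly true: response dates and withdrawal reasons are recorded. The start date of the new drug is not required, so attribution could remain uncertain.
- **Censoring at new therapy is not the only sound choice.** This stands for duration of response and PFS. Such censoring can be informative, and following patients to progression regardless of later therapy is a legitimate alternative.

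A reader might infer three stronger things that the documents do not support:
- That PFS is written so as to credit disease control on the next drug. No PFS window is written at all; the defect is the missing definition.
- That the clinical benefit rate is inflated in the same way. A patient who stops with stable disease already counts, and a later partial response changes nothing. Only a patient whose first post-baseline scan comes after the new drug starts could alter that rate.
- That next-line responses will be credited. The text shows only that they could be.

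**Conclusion.** The point holds for best overall response. The stated rule, followed literally, can count a confirmed response on a later drug as a TAS-102 response. The expected inflation is 1 to 2 points, well inside the standard error of 7.3 points at a 20% rate, and it rests on an assumed 3–6 switchers and a next-line response rate of at most 10%. The reason to act is the leverage of a single case: 3.3 points on the primary endpoint, and possibly the stage 1 decision. Duration of response shares the open end, by an amount that cannot be estimated from the documents. For PFS the finding is that event and censoring rules are absent apart from the palliative-radiotherapy note. This is a modest defect, worth correcting because the correction is cheap and may not be possible afterwards.

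**What to change.** 1. In 8.2 and 11.2, state that best overall response, and stable disease for the clinical benefit rate, use only tumour assessments up to progression or the start of any new anticancer therapy, whichever is first.
2. Record the start date of the first subsequent anticancer therapy at the follow-up visits already planned in 7.5, independently of the medication recording that 5.2 ends.
3. In 11.2, define events, start date and censoring for PFS and duration of response. Name one primary rule for new therapy before documented progression (censor at the last prior assessment, count as an event, or follow through to progression), with an alternative as a sensitivity analysis.
4. Reconcile that rule with the two radiotherapy passages. Section 5.1 has patients with CNS-only progression resume protocol therapy after brain radiotherapy, while the note in 5.2 counts palliative radiotherapy as progression for PFS. The text should say how each is treated in the PFS analysis.

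The cost is protocol wording, one date field and possibly a slightly lower response rate. If the primary rule is to censor, there is also somewhat more censoring. The sample sizes of 14 and 30, the 4.4% stage 1 error and the precision do not change, and overall survival is unaffected.

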#### **For Patients with Measurable Disease (i.e., Target Disease)**

Target Lesions	Non-Target Lesions	New Lesions	Overall Response	Best Overall Response when Confirmation is Required*
CR	CR	No	CR	≥4 wks. Confirmation**

CR	Non-CR/Non-PD	No	PR	≥4 wks. Confirmation**
CR	Not evaluated	No	PR	
PR	Non-CR/Non-PD/not evaluated	No	PR	
SD	Non-CR/Non-PD/not evaluated	No	SD	Documented at least once ≥4 wks. from baseline**
PD	Any	Yes or No	PD	no prior SD, PR or CR
Any	PD***	Yes or No	PD	
Any	Any	Yes	PD	

* See RECIST 1.1 manuscript for further details on what is evidence of a new lesion.  ** Only for non-randomized trials with response as primary endpoint.  *** In exceptional circumstances, unequivocal progression in non-target lesions may be accepted as disease progression.
 
Note: Patients with a global deterioration of health status requiring discontinuation of treatment without objective evidence of disease progression at that time should be reported as “symptomatic deterioration.” Every effort should be made to document the objective progression even after discontinuation of treatment.
				

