### 2.2 Secondary

- To evaluate the qualitative and quantitative toxicities, and reversibility of toxicities, of this treatment by NCI CTC Version 4.0.3 criteria
- To determine the progression-free survival, in months, of subjects receiving TAS-102 for the treatment of unresectable or metastatic recurrent squamous cell lung cancers
- To determine the percentage of subjects who derive clinical benefit (objective response + stable disease)
- To determine the median duration of responses in months
- To determine the overall survival in months

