### 5.1 **Treatment Schedule/Administration**

All participants will have unresectable, previously-treated squamous cell NSCLC who have previously been treated with a platinum doublet (or have refused such prior therapy); those who have a molecularly targetable genetic mutation in their tumor must have also received the appropriate specific therapy for that mutation.

Both men and women of all races and ethnic groups will be eligible for this trial. This study was designed to include women and minorities, but will not be designed to measure differences of intervention effects. Men and women will be recruited with no preference to gender. No exclusion to this study will be based on race. Minorities will be actively recruited to participate.

Eligible subjects will include those with radiographically-staged locally advanced or metastatic NSCLC who have received any prior therapy for the lesion(s). Patients who receive radiation therapy to any indicator lesion must have demonstrated progressive growth of the lesion to be assessable; be willing to use contraception; are neither pregnant nor lactating; are greater than 18 years old and have an anticipated life expectancy of at least 12 weeks; have normal end-organ function and limited comorbidities, and are able to provide written informed consent.

Upon confirmation of eligibility and provision of written informed consent, subjects will receive TAS-102 (Lonsurf®) at its FDA-approved dose and schedule, 35 mg/m^2 up to a maximum of 80 mg per dose (based on the trifluridine component) orally twice daily within one hour of completion

of morning and evening meals on Days 1 through 5 and Days 8 through 12 of each 28-day cycle until disease progression or unacceptable toxicity. Doses will be rounded to the nearest 5 mg increment. Additional doses will not be taken to make up for missed or held doses. Subjects will be monitored weekly during the first cycle for tolerance, and tumor status will be assessed every other cycle. Participants will continue on therapy until the development of unacceptable toxicity, disease progression, or participant desire to discontinue protocol therapy. There is no set maximum of cycles, as patients who have responded and who are tolerating this regimen may continue it until withdrawal of consent, disease progression, development of undue toxicity, or death.

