## **7. STUDY PROCEDURES**

### 7.1 **Study Schedule of Events**

Day of Protocol	Baseline 	Day 1 Each Cycle	Day 15 Each Cycle	Day 1, odd cycles (beginning with Cycle 3)	Off Treatment	Follow Up
Studies:						
H&P / PS / VS & TOX	X	X			X	X
CBC w/ Diff.	X	X	X		X	X
CMP	X	X			X	X
UA and Pregnancy Test	X					
Diagnostic Imaging Scan / TA	X			X		X
ECG	X					
Concomitant Medications	X	X	X		X	X
Adverse Events	X	X	X		X	X
Treatment:						
TAS-102(Lonsurf®)		X				

1) Abbreviations: H&P=History and Physical examination; PS=ECOG performance status; VS=vital signs (blood pressure, temperature, pulse and respiratory rates, weight and height); TOX=toxicity assessment; CBC/diff=complete blood count and white blood cell differential; CMP=12 item complete metabolic profile (sodium, potassium, chloride, bicarbonate, blood urea nitrogen, creatinine, glucose, alkaline phosphatase, AST, ALT, total bilirubin, uric acid); UA=urinalysis; Pregnancy test only for women of childbearing potential. For the first cycle, the H&P, toxicity assessment, CBC and CMP are repeated weekly (Days 1, 8, 15 and 22).

2) Baseline studies are repeated on day 1 if there are more than 14 days between baseline and day 1. The radiographic assessment must be repeated if there are more than 21 days between baseline and day 1.

3) TA= Tumor assessment by RECIST Criteria by diagnostic CT scan, PET/CT scan and/or MRI scan. Scans are to be done within one calendar week prior to Day 1 of every odd-numbered cycle (beginning with Cycle 3).

4) TAS-102 (Lonsurf®) is initially dosed as 35 mg/m^2 up to a maximum of 80 mg per dose (based on the trifluridine component) orally twice daily within one hour of completion of morning and evening meals on Days 1 through 5 and Days 8 through 12 of each 28-day cycle. Doses will be rounded to the nearest 5 mg increment.

Follow up evaluations are also performed as appropriate clinically

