#### **First day of every odd-numbered cycle (beginning with Cycle 3):**

- CT or MRI of thorax and abdomen, or PET/CT (must be obtained within one calendar week prior to first day of each odd numbered cycle)

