## Methods for Evaluation of Measurable Disease

All measurements should be taken and recorded in metric notation using a ruler or calipers. All baseline evaluations should be performed as closely as possible to the beginning of treatment and never more than 4 weeks before the beginning of the treatment.

The same method of assessment and the same technique should be used to characterize each identified and reported lesion at baseline and during follow-up. Imaging-based evaluation is preferred to evaluation by clinical examination unless the lesion(s) being followed cannot be imaged but are assessable by clinical exam.

Clinical lesions. Clinical lesions will only be considered measurable when they are superficial (*e.g.*, skin nodules and palpable lymph nodes) and  $\geq 10$  mm diameter as assessed using calipers (*e.g.*, skin nodules). In the case of skin lesions, documentation by color photography, including a ruler to estimate the size of the lesion, is recommended.

Chest x-ray. Lesions on chest x-ray are acceptable as measurable lesions when they are clearly defined and surrounded by aerated lung. However, CT is preferable.

Conventional CT and MRI. This guideline has defined measurability of lesions on CT scan based on the assumption that CT slice thickness is 5 mm or less. If CT scans have slice thickness greater than 5 mm, the minimum size for a measurable lesion should be twice the slice thickness. MRI is also acceptable in certain situations (*e.g.* for body scans).

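### The four-week minimum for stable disease runs from the baseline scan and never binds at a scheduled scan, so an early unscheduled reading can count as clinical benefit despite progression at the first scheduled scan

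*Combined protocol and SAP*

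**What the plan says.** Section 8.2, in the table for patients with measurable disease, accepts SD as best overall response when it is "Documented at least once ≥4 wks. from baseline". A footnote limits this condition to non-randomized trials with response as the primary endpoint, which this trial is. The text before the table takes the best response recorded up to progression, and the table's progression row applies only where no SD, PR or CR came first.

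The age of the baseline scan is set in Section 7.1, footnote 2: "The radiographic assessment must be repeated if there are more than 21 days between baseline and day 1". On-study scans start with Cycle 3 and, under Section 7.3, "must be obtained within one calendar week prior to first day of each odd numbered cycle". A note under the Section 7.1 schedule allows further evaluations where clinically appropriate.

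Sections 2.2 and 11.2 count SD, with CR and PR, toward the clinical benefit rate. Two evaluability rules exist. Section 8.1 asks for at least one cycle plus a re-evaluation of disease. Section 11.1 asks for two cycles as planned. Section 11.2 does not say which of them sets the denominator of the clinical benefit rate.

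**The concern.** A minimum time for SD is meant to ensure that the disease has been observed as stable on treatment for a useful period. Here part of the four weeks can pass before the first dose, so the requirement can be met after about a week of treatment. It also has no link to the scan schedule: every scheduled scan satisfies it automatically. It can make a difference only when someone orders a scan early.

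Since SD stands once recorded, two patients with the same tumor course can be classified differently. Both have progressed by the first scheduled scan, but the one who had an extra early scan counts as having clinical benefit. The clinical benefit rate would then depend partly on how often unscheduled scans are done, and the effect can only raise it.

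**Working it through.** The plan states no minimum time on treatment before SD counts, so there is no figure of its own to reproduce. The stage-one error in Section 11.1 concerns objective responses and is not an input.

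**Inputs**
- SD minimum: 4 weeks = 28 days from baseline (Section 8.2 table).
- Oldest permitted baseline scan at Day 1: 21 days (Section 7.1, footnote 2).
- Dosing: "Days 1 through 5 and Days 8 through 12 of each 28-day cycle" (Section 5.1).
- First scheduled scan: up to 7 days before Cycle 3 Day 1 (Sections 7.1 and 7.3).
- Evaluability: one cycle plus re-evaluation (Section 8.1) or two cycles (Section 11.1).
- Evaluable subjects: 14 at stage one, 30 in total (Section 11.1).

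**Step 1. Earliest SD reading.** Days after Day 1 = 28 − age of the baseline scan.

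| Age of scan at Day 1 (days) | Earliest SD, days after Day 1 |
|---|---|
| 0 | 28 |
| 7 | 21 |
| 14 | 14 |
| 21 | 7 |

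Seven days after Day 1 is Day 8. Five dosing days (Days 1 to 5) come before it.

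**Step 2. First scheduled scan.** Cycle 3 Day 1 = 1 + 2 × 28 = Day 57. The window opens at 57 − 7 = Day 50. This is 49 to 56 days after Day 1. Counted from the baseline scan it is 49 to 56 days if that scan was done on Day 1, and 49 + 21 = 70 to 56 + 21 = 77 days if it was 21 days old. All of these exceed 28, so the minimum is always already met. A delay in Cycle 3 only lengthens the interval.

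**Step 3. One patient followed through.**
- The baseline scan is 21 days before Day 1. An unscheduled scan on Day 8 is read as SD: 21 + 7 = 28 days from baseline, so it qualifies.
- The patient completes Cycle 1 and takes the Cycle 2 doses, which end on Day 28 + 12 = Day 40. A scan at the end of Cycle 2 finds the patient evaluable under Section 8.1 and also under Section 11.1.
- That scan, the first scheduled one, shows progression.
- Best response up to progression is SD, so the patient counts toward clinical benefit.
- Without the Day 8 scan, the same patient's best response is progression, and the patient does not count.

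**Step 4. Size per patient.** 1/30 = 3.3 percentage points and 1/14 = 7.1 percentage points.

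**The case against.** The strongest reply is that the evaluability rules already supply a longer floor. A reader might infer from Step 1 that a patient who received about one week of drug in total could be counted as deriving clinical benefit. The documents do not support that: such a patient fails the one-cycle rule in Section 8.1 and the two-cycle rule in Section 11.1. A patient who fails before Day 50, with two full cycles not completed, is likewise outside the Section 11.1 set and could count only under Section 8.1, after a full cycle. This part of the reply stands. It does not dispose of the point, because the rules decide who is analyzed and not how long disease must have been stable. The patient in Step 3 meets both.

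Four other strong readings also go too far.
- Section 8.1 has baseline evaluations "never more than 4 weeks before the beginning of the treatment", and 28 − 28 would give zero days on treatment. A site that follows both limits must repeat any scan older than 21 days, so the zero-day case does not arise.
- Section 8.2, under Duration of Response, says "Stable disease is measured from the start of the treatment until the criteria for progression are met". This defines how long SD lasts, whereas the table defines when SD may be assigned. The two differ in starting point, but the first is not a competing minimum.
- A total inflation of several points might be inferred. The documents give no frequency of early scans, and any assumed percentage of such patients simply reappears as the same number of points.
- A bias against the figure of about 50% in Section 1.1 might be inferred. That section gives no SD definition, and Section 11.2 plans only estimation with exact intervals.

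Finally, no on-treatment scan is planned before Day 50, and the provisions for clinically indicated evaluations read most naturally as concerning follow-up. Early scans are not prohibited, but they may be rare.

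**Conclusion.** The point holds within narrow limits. The SD minimum can be met from Day 8, never acts at a scheduled scan, and lets an early unscheduled SD reading stand as clinical benefit when the first scheduled scan shows progression. The effect is upward only, at 3.3 percentage points per such patient at n = 30 and 7.1 at n = 14. The number of such patients cannot be derived from the documents and is probably low.

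Only the secondary clinical benefit rate is affected. The primary response rate and the 14/30 rule are unchanged.

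The conclusion rests on three assumptions: baseline in the table means the date of the baseline scan, which Section 7.1 supports by separating baseline from Day 1; unscheduled scans on treatment are read under RECIST and enter best response; and the Day 50 to 57 window assumes that cycles start on time.

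**What to change.** In the Section 8.2 table and in Section 11.2, state that SD counts toward clinical benefit only if documented at the first scheduled assessment or later, which is at least 49 days after Cycle 1 Day 1. State the consequence as well: progression at that assessment after only an earlier SD reading is not clinical benefit. Because cycles can be delayed, the text should say that the scheduled assessment governs and that 49 days is its earliest date.

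Reconcile the one-cycle rule in Section 8.1 with the two-cycle rule in Section 11.1, and name the denominator of the clinical benefit rate in Section 11.2. Say how patients with only earlier scans are counted. This has to be settled together with the evaluability rule, since counting them as having no benefit would bring into the denominator patients whom the two-cycle rule leaves out. Running the four weeks from Day 1 would also remove time before treatment from the minimum, but 28 days would still fall short of the first scheduled scan.

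The change adds no scans and leaves the design as it is. The clinical benefit rate may come out slightly lower.
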